#### **4.5. Participant withdrawal**

Participants are welcome to withdraw from the study at any time. Researchers will ask the reason for their withdrawal, and whether they are withdrawing from study treatments (UCBC infusion if they withdraw immediately after screening and baseline assessment) and/or the follow up assessments. If families agree to continue with the follow-up, researchers (either site PI or study coordinator) will contact participant families at each follow up assessment point by phone to arrange the assessment. Families that have previously withdrawn and have asked for no further contact will be excluded from this process. The timing and reasons for withdrawal will be documented in all cases.

Researchers may need to withdraw a participant for the participant's safety, for example if a serious adverse event occurs during infusion that prevents completion of the infusion. Additionally, if the study is terminated for any reason, all participants will be withdrawn. If participants require excluded medical procedures, such as surgery prior to the UCBC infusion, they will be withdrawn, but if the excluded medical procedures are required after the UCBC infusion the protocol violation will be recorded and reported but the participant will not be withdrawn from the study.

Regardless of when or why the participant withdraws, they will be offered medical assistance and follow up for the duration of the study to ensure the participant's safety.

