#### 4.3. Primary and secondary outcome measures

The primary objective of this study is to collect initial safety data during and after infusion of sibling UCBCs. The following outcomes will be collected to assess this objective which will be assessed at three time points:

- 1) During the infusion and up to 36 hours after
  - Clinical assessment, including vital signs and pulse oximetry
  - Laboratory assessment looking for markers of infection

- Occurrence of AEs and SAEs
- 2) Within the three months after infusion
  - Clinical assessment
  - Laboratory assessment looking for markers of immune reaction
  - Deterioration of motor function as assessed by Gross Motor Function Measure
  - Occurrence of AEs and SAEs
- 3) Within the 12 months after infusion
  - Clinical assessment
  - Deterioration of motor or cognitive function as assessed by the appropriate tool (see section 7.3)
  - Occurrence of AEs and SAEs

The secondary outcomes include:

- Efficacy of the intervention at 3 months measured by therapists on a suite of standardised psychometrically sound measures of movement, cognition and quality of life. This will be assessed in an exploratory fashion only. The areas for assessment were selected to focus on motor outcomes because CP is a primarily motor disorder; on cognitive outcomes that have shown change in an international trial [49] and anecdotally from private stem cell clinics (changes in wakefulness, attentiveness and alertness have been described); and how these might affect the participant's life; The motor and quality of life outcomes will also be measured at 3 months. Cognition will be measured at 12 months after infusion and used to calculate change from baseline. Again, the analysis of the 12 month data will be exploratory in nature.
- Understanding the longevity of infused cells. This will be achieved using chimerism studies (engraftment analysis), looking for infused cells circulating in a sibling recipient's blood. We will study chimerism by extracting circulating cell free DNA from plasma and using a new quantitative PCR method detecting differences in copy number deletions between the recipient and donor. It will be reported as the fraction of donor DNA in the sample at each time point for each individual, and constitutes both a safety and mechanistic study.

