## 6. STUDY VISITS AND PROCEDURES SCHEDULE

Study phase	Enrolment	Baseline	Infusion	Follow up					
Visit number	1	2	3	4	5	6	7	8	9
Timing	> 8 wks prior to infusion	21 days prior to infusion	0	1 day	1 wk	1 mo	3 mo	6 mo	12 mo
Tolerance	Any time	> 3 wks since Visit 1	- Within 10-30 days of clear virology screen - CBU available	± 0 days	±2 days	± 7 days	± 2 wks	± 2 wks	± 2 wks
Location	Hospital	Hospital	Hospital	Hospital	Hospital, home	Hospital	Hospital	Hospital, community	Hospital
Informed consent (45 mins)	X								
CP assessment (30 mins)		X							
Medical history (0.5 hr)		X							
Physical examination (0.5 hr)		X	X	X		X	X	X	X
Medical assessment (10 mins)				X	X	weekly	X	X	X
Assessment of motor function (45 mins)		X					X		X
Assessment of upper limbs (15 mins)		X					X		X
Assessment of quality of life (0.5 hr)		X					X		X
Assessment of cognition (2hr 15)		X							X
Infusion of UCB (30 mins)			X						
Intravenous fluids, observation (6 hrs)			X						
Anti-D administration if required (5 mins)				X					
Blood collection	X	X	2X	X	X	X	X		
Rehabilitation Therapy									
Length of visit	1 hr	6 hrs (may need two visits)	9 hrs	1 hr	1 hr	1 hr	2 hrs	1 hr	4 hrs

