#### Medical assessment

Medical assessment will be conducted at 1 day, weekly until 1, 3 and 12 months after infusion, and at any time that the participant or their family feel concerned. All medical assessments will be conducted by a transplant specialist. It comprises a short list of questions of participant safety over the phone from the trial doctor, focused on signs of infection and inflammation. Should the participant show any indication of needing more detailed examination, they will be asked to return to the infusion hospital as soon as possible. If necessary, they may of course attend their nearest medical service and the trial doctor will follow this up.

At visit 6 (6 months post infusion), a paediatrician either at a trial site hospital or in the local community will conduct a general health assessment of the participant.

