#### Cognitive assessment (baseline and at visit 9)

No specific cognitive training programs have been validated for use with children with CP, however the limited evidence available indicates there may be some spontaneous improvement in cognition. Therefore, cognition will be assessed by a psychologist in an age appropriate manner (see Table 2 below), ensuring that an individual is tested using the same tool before and after the intervention. There is a possible learning effect with cognitive assessment tools, in that using them too often leads to familiarity with the tool which confounds data on actual change in cognition, therefore most tools are recommended for use only every 12 months. Therefore, we will avoid assessing cognition at the 3 and 6 month assessment visits but will assess at baseline (-1 month) and 12 months. Note that this assessment may not be possible for children with extremely severe CP. 1 hour to administer (participant)

Table 2: Cognitive assessment tools for each age range.

Age Range (at baseline)	Assessment tool
1-2.5 years (validated 3-42 months)	Bayley Scales of Infant and Toddler Development 3 rd Edition (Bayley-III)
>2.5-6 years (validated 2.5–7 years)	Wechsler Preschool Primary Scale of Intelligence (WPPSI–IV)
>6 years (validated 6-16 years)	Wechsler Intelligence Scale for Children (WISC-IV, or WISC-V if released prior to trial commencement)

The Vineland Adaptive Behaviour Scales (Vineland-II) assesses personal and social skills needed for everyday living and is validated for use across the lifespan (birth-90 years). This assessment will be used in the parent/caregiver reporting format for all participants, to allow use for children with severe CP who would not be able to complete the assessment on their own behalf. 30 mins to administer (parent)

The Behaviour Rating Inventory of Executive Function (BRIEF) will be used to provide information on how problems such as attention difficulties, poor working memory, disinhibition and planning/organisational impairments impact everyday behaviour. The BRIEF is used for 5-18 year olds, the preschool version BRIEF-P is used for 2-5 year olds. It is a parent questionnaire of 86 items. 15 mins to administer (parent)

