### Eliciting Adverse Event information

Adverse events will be recorded from the time of infusion until the last visit (12 months post infusion). During the UCBC infusion patients will be monitored at 5 minute intervals, then during hydration every 30 minutes. On leaving the hospital, the patients and their families will be provided with contact details and

asked to contact the study team if any unusual health change should occur. They will also be provided with a card to provide to a treating doctor should the participant require an unscheduled visit, particularly other than at the study site hospital. The card provides details for either the family or the admitting doctor to notify study doctors of potential SAEs to ensure information is elicited, and reported, as early as possible.

The transplant physician will conduct a medical assessment on the day after infusion to assess late reactions to infusion (eg. fever, signs of renal insufficiency), and each week (to detect signs of GvHD) until the 1 month follow up physical examination. At each study visit patients will be asked how they feel and how they have felt in the period since the last visit. They will also be asked if they have had any accidents, illnesses, been hospitalised or changed medication. AEs will also be documented from findings of physical examination.

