#### *Assessment and Documentation of Adverse Events*

AEs will be reported to the investigator by the infusion team, family or assessing paediatrician or therapist. The investigator is then responsible for recording all AEs, regardless of their association with the study.

The documentation of each AE will include a description of the AE and its severity, timeline, action or treatment required and the outcome. After discussion with the study team, the likelihood that the AE was the result of the study intervention will be assessed as unrelated, possible, probable or definite.

All AEs will be followed until resolved, and changes in the AE or repeated episodes will be documented for retention and publication.

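### Does withdrawing every participant when the study is terminated cut short the safety record of children already infused?

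*Protocol*

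**What the plan says.** Section 4.5 of the Protocol lists several routes to withdrawal: the family's choice, the child's safety, termination of the study, and an excluded procedure needed before infusion. On termination it says "Additionally, if the study is terminated for any reason, all participants will be withdrawn". It closes with a general offer: "Regardless of when or why the participant withdraws, they will be offered medical assistance and follow up for the duration of the study", and gives the participant's safety as the reason.

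Section 4.3 lists among the 12-month outcomes for the primary safety objective "Deterioration of motor or cognitive function as assessed by the appropriate tool". The cognitive part can be measured only once after infusion, because Section 7.3 says "we will avoid assessing cognition at the 3 and 6 month assessment visits but will assess at baseline (-1 month) and 12 months".

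Section 8 sets the recording rules: "Adverse events will be recorded from the time of infusion until the last visit (12 months post infusion"), and "All AEs will be followed until resolved". It also says that GvHD of Grade II or above stops the trial, and that the monitoring committee may advise stopping for other serious events. Section 7.1 adds medical assessment "at any time that the participant or their family feel concerned".

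**The concern.** In a first safety study of this product, children already infused are the whole source of information, and they matter most if the trial stops early. The termination sentence covers all of them. The section shows that it can write an exception, since a child who needs an excluded procedure after infusion stays in the study. It also separates withdrawal from treatment and withdrawal from follow up without saying which one termination brings about. With a single infusion, follow up is the main thing an infused child has left to be withdrawn from.

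The closing offer is tied to the duration of the study, and that has no stated end once a study has been terminated. If it ended at termination, a stop triggered by GvHD in one child would end observation of the others just when it was most needed. The 12-month safety window would be incomplete, and cognitive deterioration might not be assessed in any child.

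**Working it through.** The plan gives no figure to reproduce on this point. The check has two parts: the size of the loss on the unfavourable reading, and which reading the text supports.

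**1. Size if observation ended at termination.** Section 6 schedules six visits after infusion: visit 4 (1 day), 5 (1 week), 6 (1 month), 7 (3 months), 8 (6 months) and 9 (12 months). Motor function is assessed at visits 7 and 9, cognition at visit 9 only. The unobserved share after month t is (12 − t)/12.

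| Termination just after | Months unobserved | Visits lost | Motor done | Cognitive done |
|---|---|---|---|---|
| 1-month visit | 11/12 = 92% | 3 of 6 | 0 of 2 | 0 of 1 |
| 3-month visit | 9/12 = 75% | 2 of 6 | 1 of 2 | 0 of 1 |
| 6-month visit | 6/12 = 50% | 1 of 6 | 1 of 2 | 0 of 1 |

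Visit 9 has a tolerance of 2 weeks either side, so the earliest 12-month visit falls about 11.5 months after the first infusion. A termination before then would leave no child with complete 12-month observation. If follow up continues as planned, every loss in the table is 0.

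**2. What study duration means in this protocol.** Section 4.2 is the section on expected duration. It gives 2 years, running to final follow up and data analysis. Its components can be added up. Recruitment and screening take 3 months. The first group is infused over 1 month and followed for 3 (4 months). The second group takes the same (4 months). The last six are infused over 1 to 2 months (my assumption; the section gives one month per group of three). Follow up of the last child takes 12 months.

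3 + 4 + 4 + 1 + 12 = 24 months, or 3 + 4 + 4 + 2 + 12 = 25 months.

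The stated duration is therefore about the time the last infused child needs to reach 12 months. Follow up offered for that duration reaches, or very nearly reaches, every child's 12-month visit.

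**3. The two readings side by side.**

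- *Duration means the planned period.* The closing offer in Section 4.5 then has content for every route to withdrawal listed above it, termination included.
- *Duration ends at termination.* The offer then has zero length for participants withdrawn by termination. Yet the sentence says it applies whatever the reason, and termination is one of the reasons just given.

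The second reading empties a sentence written to protect participants, so the first is the natural one.

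**4. Whether what is seen is recorded.** Section 8 fixes the adverse event window by time since infusion, up to 12 months. It makes the investigator responsible for recording every event and has events followed to resolution. None of these rules makes an exception for termination. They do not conflict with Section 4.5, and Section 4.5 need not repeat them.

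**The case for a change.** The strongest case for a change is that the remaining gap concerns outcomes under the primary objective. Section 8 secures adverse events, but it does not address a child withdrawn by termination, and following events to resolution covers only events already identified. Nothing says expressly that the scheduled motor and cognitive assessments go on. An early stop is foreseeable, because GvHD of Grade II or above stops the trial. A clarifying sentence would be short. The remaining visits for a child past 3 months take 1 + 4 = 5 hours, so at most 12 × 5 = 60 hours for all twelve, and all of it is already planned.

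Part of this stands. Section 4.5 is silent on the scheduled assessments, and its procedure for arranging them by phone is written for families who choose to withdraw. But silence is not a wrong rule. Section 4.5 offers follow up, Section 6 says what follow up consists of, and Section 4.5 already shows how visits are arranged for withdrawn families who agree. An investigator facing a termination would use these.

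Two further points reduce what a change could gain. If termination followed loss of funding or of ethics approval, continued assessment might be impossible whatever Section 4.5 said. And the first six children infused are GMFCS IV or V (Section 4), while Section 7.3 notes that cognitive assessment may not be feasible in extremely severe CP. Some of the cognitive data at stake might not exist even in a completed trial, although the caregiver-reported scales would.

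The varying use of stopping and terminating across Sections 4.5 and 8 is ordinary usage. It produces no conflicting instruction.

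**Conclusion.** The concern does not call for a change. Section 4.5 leaves a phrase undefined and does not state outright that scheduled assessments continue after termination. Read with Sections 4.2, 6 and 8, it means that infused children are offered follow up over the planned period and that adverse events are recorded to 12 months. On that reading nothing is lost. The losses of 92%, 75% and 50% of the 12-month window arise only if study duration is taken to end at termination, which would make the safety offer meaningless in one of the cases it covers. The conclusion rests on reading the protocol as a whole, and on families agreeing to continue and ethics approval remaining in place. Section 9 presents results descriptively, so even the unfavourable reading would affect the completeness of the safety record and not an inference. This is a gap that investigators and analysts would fill sensibly.

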### **5. STUDY PROCEDURES**

#### **5.1. Recruitment**

In order to distribute information about this study, researchers will provide a description of the trial to CP registers and community organisations and to private cord blood banks (Appendix 1: Information to go in newsletters).

- Researchers will ask CP registers to publish details of this trial in their newsletters and invite families to contact researchers.
- Researchers will ask community organisations to distribute the information as appropriate.
- The private cord blood banks will notify their clients of this trial and invite families to contact researchers.

Recruitment through clinicians and allied health professionals will be welcomed. Our experience is that there are many families who are interested in stem cell therapy and have brought this to the attention of their clinicians. Researchers will therefore make information available by providing the Australasian Academy of Cerebral Palsy and Developmental Medicine (AusACPDM) with information to circulate to clinicians and allied health professionals working in the field of CP. Thus, if families approach their clinicians and allied health professionals to discuss the trial, the professionals will have some understanding. Making information available for health professionals will also be valuable for later in the trial, particularly in areas of Australia far from infusion sites.

Families that contact the study team will be verbally informed about the trial by the lead site study coordinator, will have the opportunity to ask questions and will be informed of eligibility requirements. Researchers will ask for verbal consent to record some details about the potential participant in the study database (does the child have CP, do they have an immune deficiency, did they store cord blood at birth of any child, which child, where, family contact details; see Appendix 2: Script for first contact phone conversation, Appendix 3: Record of verbal consent, and Appendix 4: Letter following verbal consent).

If families believe they donated the potential participant's sibling UCB, and they would like to find out if the CBU is recorded at a CBB, researchers will mail the family a template letter (Appendix 5: Template to ask CBB to locate CBU records) which explains the purpose of the requested CBU search, has space for the family to fill in required details including the participant's sibling's date of birth, hospital of birth, sex and mother's details, and a signature constituting consent for the CBU search and for the CBB to provide researchers with results of the CBU search. A second copy of the template letter will be included for

families to retain as a record of their consent, and a reply-paid envelope for families to mail the first copy to researchers (rather than directly to a CBB, to preserve CBB independence from the trial). Once researchers receive this template letter as consent, the trial coordinator will provide the appropriate CBB with a copy so that they are able to locate a record of the CBU. Families will be notified of the outcome of the record search by phone. The details from those who verbally consented during the initial phone call, and signed consent following the record search will be recorded in the study database as part of initial recruitment data.

Once the CBU record search is complete, the lead site study coordinator will phone to provide the results of the search, to discuss the next steps with potential participant families (Appendix 6: Script for phone conversation after CBU record search, or part of the above phone call if appropriate) and to encourage families to discuss the trial with their clinician. An Information Statement without the consent form will be mailed to families so that families can continue considering their involvement in the trial. Families will be able to contact the lead site study coordinator or researchers to ask questions and discuss the study. If they choose to enrol, they must contact the lead site study coordinator or researchers to arrange an initial visit to an infusion hospital for the participant and family for informed consent. During this phone contact, the trial coordinator will inform families of the current number of places available within the trial and will estimate the likelihood that the potential participant will continue through the trial, and will request confirmation of the child's diagnosis (Appendix 7: Script for phone conversation to arrange Visit 1, Appendix 8: Letter to family to request confirmation of diagnosis).

If needed, and if the family consent, a letter and copy of the signed form (Appendix 8:) will be mailed to the nominated child's doctor asking for information (Appendix 9: Letter to child's doctor requesting information). If a family does not provide documentary evidence of CP diagnosis or consent to contact with a diagnosing or treating doctor, they may discuss it with the study doctor. If the family do not provide a reasonable justification for the lack of CP diagnosis, the child may be excluded. If the family provides reasonable justification, the child may require assessment by a paediatrician after Informed Consent, but prior to other study procedures. This will be at the discretion of the study doctor.

A record of all participants that were pre-screened or enrolled by researchers will be sent to and kept by the lead site study coordinator, including reasons for ineligibility or non-participation if available, to inform future trial design. All participants who do not receive the intervention will also be asked whether they would like to be contacted about any appropriate future trials, and they will be informed that future trials may focus on younger children. The custodian of this databank will be the lead site study coordinator at the lead site until the conclusion of the trial, at which time custodianship will shift to the coordinating principal investigator.

